10.3 Appendix 3: Contraceptive Guidance and Collection of Pregnancy Information

Females of childbearing potential (FOCBP) are females whose menstruation has started and who are not documented as sterile (eg, have had a bilateral oophorectomy, or hysterectomy, or who have been postmenopausal for at least 12 months). Females of non-childbearing potential do not meet definition of FOCBP.

For males and FOCBP, or their partners, who are sexually active, there must be a documented agreement that the subject and their partner will take effective measures (ie, 2 different approved methods of birth control or remain abstinent) to prevent pregnancy during the course of the trial and for 90 days after the last trial intervention administration. Unless the subject is sterile (ie, females who have had a bilateral oophorectomy, have had a hysterectomy, or have been postmenopausal for at least 12 consecutive months; or males who have had a bilateral orchiectomy) or remains abstinent during the trial and 90 days after the last trial intervention, 2 of the following approved methods of birth control must be used: vasectomy, tubal ligation, nonhormonal intrauterine device, birth control pill, birth control implant, birth control depot injection, birth control patch, condom with spermicide, sponge with spermicide, or occlusive cap (vaginal diaphragm or cervical/vault cap) with spermicide. Concomitant use of carbamazepine with hormonal contraceptive products (eg, oral and levonorgestrel subdermal implant contraceptives) may render the contraceptives less effective because the plasma concentrations of the hormones may be decreased. Breakthrough bleeding and unintended pregnancies have been reported. For FOCBP enrolled in Part 2 of the trial, if employing birth control, 2 of the following precautions must be used: vasectomy, tubal ligation, nonhormonal intrauterine device, condom with spermicide, sponge with spermicide, or occlusive cap (vaginal diaphragm or cervical/vault cap) with spermicide. Any single method of birth control, including vasectomy and tubal ligation, may fail, leading to pregnancy. The contraceptive method will be documented in the eCRF or source document. Male subjects must also agree not to donate sperm from trial screening through 90 days after the last trial intervention administration.

Before enrolling males and females in this clinical trial, investigators must review the following information about trial participation as part of the ICF process. The topics should generally include:

- General information
- Informed consent form
- Pregnancy prevention information
- Contraceptives in current use

- Follow-up of a reported pregnancy

Before trial enrollment, males and FOCBP must be advised of the importance of avoiding pregnancy during trial participation and the potential risk factors for an unintentional pregnancy. Subjects must sign the ICF confirming that the above-mentioned risk factors and the consequences were discussed.

A urine or serum pregnancy test for human chorionic gonadotropin will be performed at screening and at check-in to the inpatient facility on all FOCBP. If a urine test is performed and is positive, the investigator will follow-up with a confirmatory serum test.

During the trial, all FOCBP should be instructed to contact the investigator immediately if they suspect they might be pregnant (eg, missed or late menstrual cycle). Male subjects must be instructed to contact the investigator immediately, during the trial, if their partner suspects that they might be pregnant (eg, missed or late menstrual cycle).

If a subject is suspected to be pregnant before she receives trial intervention(s), the intervention administration must be withheld until the results of serum pregnancy tests are available. If the pregnancy is confirmed, the subject must not receive the trial intervention(s) and must not be enrolled in the trial. If pregnancy is suspected while the subject is taking trial intervention(s), the intervention(s) must be withheld immediately (if reasonable, taking into consideration any potential withdrawal risks) until the result of the pregnancy test is known. If pregnancy is confirmed, the trial intervention(s) will be permanently discontinued in an appropriate manner (eg, dose tapering if necessary for subject safety) and the subject will be withdrawn from the trial. Exceptions to trial discontinuation may be considered for life-threatening conditions only after consultations with the IRE contact (see the title page of this protocol for contact information).

[figure not shown]
The investigator must immediately notify the sponsor (within 24 hours) of any pregnancy associated with trial intervention exposure during the trial and for at least 90 days after the last trial intervention administration and record the event on the IRE form and forward it to the sponsor. The sponsor will forward the Pregnancy Surveillance Form(s) to the investigator for monitoring the outcome of the pregnancy.

Protocol required procedures for trial discontinuation and follow-up must be performed on the subject unless contraindicated by pregnancy (eg, x-ray studies). Other appropriate pregnancy follow-up procedures should be considered if indicated. In addition, the investigator must report to the sponsor, on the Pregnancy Surveillance Form(s), follow-up information regarding the course of the pregnancy, including perinatal and neonatal outcome. Infants will be followed for a minimum of 6 months from the date of birth.

10.4 Appendix 4: Protocol Amendments

The investigator will not make any changes to this protocol without the sponsor's prior written consent and subsequent approval/favorable opinion by the IRB. Any permanent change to the protocol, whether an overall change or a change for specific trial site(s), must be handled as a protocol amendment. Any amendment will be written by the sponsor. Each amendment will be submitted to the IRB, as required by local regulations. Except for "administrative" or "non-substantial" amendments, investigators will wait for IRB approval/favorable opinion of the amended protocol before implementing the change(s). Non-substantial amendments are defined as having no effect on the safety of subjects, conduct or management of the trial, trial design, or the quality or safety of intervention(s) used in the trial. A protocol change intended to eliminate an apparent immediate hazard to subjects should be implemented immediately after agreement by the sponsor and investigator, followed by IRB notification within local applicable timelines. The sponsor will submit protocol amendments to the applicable regulatory agencies within local applicable timelines.

When the IRB, investigators, and/or the sponsor conclude that the protocol amendment substantially alters the trial design and/or increases the potential risk to the subject, the currently approved written ICF will require similar modification. In such cases, after approval/favorable opinion of the new ICF by the IRB, repeat written informed consent/assent will be obtained from currently enrolled subjects in the trial before the amendment-specified changes in the trial are implemented.

11 References

- ¹ Otsuka Pharmaceutical Development and Commercialization, Inc. OPC-167832 Investigator's Brochure, Edition 7. Otsuka Report, issued 28 Feb 2022.
- ² Yamamura Y. Identification of human cytochrome P450 isoforms involved in metabolism of 14C-OPC-167832 by recombinant human cytochrome P450s. Otsuka Study No. 038119, Otsuka Report No. 031575, 2015.
- ³ Yamamura Y. Recognition of 14C-OPC-167832 by human P-gp and inhibitory potential of OPC-167832 on quinidine transport in the human P-gp expressing LLC-PK1 cells. Otsuka Study No. 038811, Otsuka Report No. 032277, 2016.
- ⁴ Yamamura Y. Recognition of 14C-OPC-167832 by human BCRP and inhibitory potential of OPC-167832 on prazosin transport in the human BCRP expressing MDCKII cells. Otsuka Study No. 039110, Otsuka Report No. 032584, 2017.

QT	part of an ECG wave pattern (from QRS to T)
QTcB	QT Interval Bazett's formula
QTcF	QT Interval Fredericia's formula
RBC	Red blood cell
RR	inter-beat interval
SAE	Serious adverse event
TEAE	Treatment-emergent adverse event
t_{\max}	Time to maximum (peak) plasma concentration
ULN	Upper limit of normal

Quabodepistat (OPC-167832)

Study 323-201-00007

1 Introduction

This statistical analysis plan (SAP) documents the statistical methodology and data analysis algorithms and conventions to be applied for reporting of pharmacokinetics and safety data of Trial 323-201-00007. This is an open-label trial and no blinding/unblinding processes are used in this trial.

2 Trial Objectives

The primary objectives are: to assess the potential for CYP-mediated drug-drug interactions with OPC-167832:

- Inhibition of OPC-167832 metabolism via CYP3A by itraconazole.
- Induction of OPC-167832 metabolism via CYP3A by carbamazepine.

The secondary objectives are: to assess the safety and tolerability of OPC-167832 administered alone or in combination with itraconazole or carbamazepine

3 Trial Design

This is a single-center, 2-part, open-label, non-randomized single arm, drug-drug interaction (DDI) trial in healthy adult subjects. Part 1 (OPC-167832, itraconazole) and Part 2 (OPC-167832, carbamazepine) will have fixed sequence designs with 12 subjects in each part for a total of 24 subjects enrolled.

3.1 Type/Design of Trial

Following a screening period of up to 28 days, eligible subjects will enter the clinic (check-in) on the day prior to the first treatment day (Day -1).

For Part 1, the impact of CYP3A inhibition on the PK of OPC-167832 will be assessed. Subjects will receive a single, 30 mg, oral dose of OPC-167832 CCI in the fasted state on Day 1 with blood collections for PK assessment of OPC-167832 from Day 1 through Day 8. On Day 8, subjects will receive 200 mg doses of itraconazole in the morning and evening (200 mg twice daily [BID]) followed by 200 mg of itraconazole administered once daily on Day 9 through Day 14 to approach steady-state conditions for itraconazole. On Day 15, a single, 30 mg, oral dose of OPC-167832 CCI will be administered concurrently with a 200 mg dose of itraconazole in the fasted state with blood collections for PK assessment of OPC-167832 from Day 15 through Day 26. Once daily 200 mg doses of itraconazole will continue to be administered on Day 16 through Day 25. Subjects will be discharged from the clinic after the PK sample on Day 26 or early termination (ET).

Quabodepistat (OPC-167832)

Study 323-201-00007

For Part 2, the impact of CYP3A induction on the PK of OPC-167832 will be assessed. Subjects will receive a single, 30 mg, oral dose of OPC-167832 CCI on Day 1 in the fasted state with blood collections for PK assessment of OPC-167832 from Day 1 through Day 8. On Day 8 through Day 10, subjects will receive 100 mg BID carbamazepine followed by 200 mg BID carbamazepine administration on Day 11 through Day 13 and 300 mg BID carbamazepine administration on Day 14 through Day 31. On Day 25, a 30 mg oral dose of OPC-167832 CCI will be administered concurrently with the morning 300 mg dose of carbamazepine in the fasted state with blood collections for PK assessment of OPC-167832 from Day 25 through Day 32. Subjects will be discharged from the clinic after the PK sample on Day 32 or ET.

All subjects will be contacted by phone 30 days after the last dose of OPC-167832 to assess any new or ongoing AEs and to record concomitant medications.

3.2 Trial Treatments

OPC-167832, itraconazole, and carbamazepine will be administered orally to subjects as per the dosing schedule below. OPC-167832 CCI will be provided as 30 mg tablets, itraconazole will be administered as a 10 mg/mL oral solution, carbamazepine will be administered as the least number of tablets based on commercially available extended-release tablets (ie, 100 mg tablet, 200 mg tablet). Lower dose strengths of carbamazepine can be combined, ie, a 100 mg tablet and a 200 mg tablet should be combined to dose at 300 mg. All doses will be administered with approximately 240 mL of room temperature, still water. When itraconazole is administered, some of the 240 mL of water should be used to rinse the dosing container. All doses of OPC-167832 (administered on Days 1 and 15 in Part 1 and Days 1 and 25 in Part 2) will be administered following an overnight fast of at least 10 hours.

For Part 1, OPC-167832 and itraconazole will be administered in the morning at the same time each day. The BID dose of itraconazole on Day 8 will be administered every 12 hours (q12h). On days of serial PK sampling days (Days 1 and 15), subjects will be required to continue to fast from food for at least 4 hours following dosing of OPC-167832 and water will be restricted for 1 hour before to 2 hours after dosing of OPC-167832. Water is permitted ad libitum on all other days.

For Part 2, OPC-167832 and carbamazepine will be administered in the mornings at the same time each day and BID doses of carbamazepine will be administered q12h and at same time each evening. On days of serial PK sampling days (Days 1 and 25), subjects will be required to continue to fast from food for at least 4 hours following dosing of

Quabodepistat (OPC-167832)

Study 323-201-00007

OPC-167832 and water will be restricted for 1 hour before to 2 hours after dosing of OPC-167832. Water is permitted ad libitum on all other days.

Table 3.2-1 Dosing Schedule		
Study Day	Time	Dose
PART 1		
1	morning	30 mg OPC-167832
8	morning	200 mg itraconazole
	evening	200 mg itraconazole
9 through 14	morning	Once-daily 200 mg itraconazole
15	morning	30 mg OPC-167832 and 200 mg itraconazole
16 through 25	morning	Once-daily 200 mg itraconazole
PART 2		
1	morning	30 mg OPC-167832
8 through 10	morning	100 mg carbamazepine extended release
	evening	100 mg carbamazepine extended release
11 through 13	morning	200 mg carbamazepine extended release
	evening	200 mg carbamazepine extended release
14 through 24	morning	300 mg carbamazepine extended release
	evening	300 mg carbamazepine extended release
25	morning	30 mg OPC-167832 and 300 mg carbamazepine extended release
	evening	300 mg carbamazepine extended release
26 through 31	morning	300 mg carbamazepine extended release
	evening	300 mg carbamazepine extended release

4 Trial Population

Twenty-four subjects in total will be enrolled in the trial, with 12 subjects enrolled in each part, such that approximately 10 healthy male or female subjects, 18 to 55 years of age, inclusive, complete each part of the trial. Discontinued subjects may be replaced at the discretion of the sponsor.

5 Sample Size

Sample size was selected assuming an intra-subject coefficient of variation for AUC of 25%, such that the point estimate of the ratio of geometric means for the PK parameters of OPC-167832 with and without coadministration of the perpetrator (itraconazole or carbamazepine) will fall within 83% and 120% of the true value with 90% confidence. Twenty-four subjects will be enrolled, 12 subjects in each part, to target approximately 10 healthy male or female subjects complete each trial part. (For definition of completer, see [Section 6.6](#)).

Quabodepistat (OPC-167832)

Study 323-201-00007

6 Statistical Analysis Sets

6.1 Efficacy Analysis Set

There are no efficacy analyses in this trial.

6.2 All Participants

All Participants includes all signatories of the informed consent form (ICF).

6.3 Enrolled Analysis Set

The enrolled analysis dataset includes all subjects that sign the informed consent form (ICF), and meet all eligibility criteria.

6.4 Safety Analysis Set

The safety dataset will include all enrolled subjects who have taken at least one dose of IMP.

In Part 1 of this trial, Investigational Medicinal Product (IMP) refers to OPC-167832 and/or itraconazole, and in Part 2 of this trial, IMP refers to OPC-167832 and/or carbamazepine.

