5.2 Eligibility Criteria

Exceptions for eligibility criteria will not be permitted during the trial, neither by the investigator nor by the medical monitor.

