9.2 Datasets for Analysis

The safety dataset includes all subjects who receive at least 1 dose of IMP.

The PK dataset will consist of all subjects who receive at least 1 dose of IMP and have at least 1 postdose evaluable plasma concentration.

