9.4.3 Safety Analyses

The safety analysis will be conducted on the safety dataset for Part 1 and Part 2, separately. Safety variables to be analyzed include AEs, clinical laboratory tests, vital signs, ECGs, physical examinations, and the C-SSRS. Summaries will be based upon subjects who took at least 1 dose of IMP. The treatment group refers to OPC-167832 alone and OPC-167832 + itraconazole/carbamazepine. Baseline will be the last available predose value at the start of the treatment period, unless otherwise defined in the statistical analysis plan.

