10.1.6 Protocol Deviations

In the event of a significant/major deviation from the protocol due to an emergency, accident, or mistake (eg, violation of informed consent/assent process, trial intervention dispensing or subject dosing error, treatment assignment error, subject enrolled in violation of eligibility criteria or concomitant medication criteria), the investigator or designee will contact the sponsor or designee at the earliest possible time by telephone or

via e-mail. The investigator and sponsor (or designee) will come as quickly as possible to a joint decision regarding the subject's continuation in the trial. This decision will be documented by the investigator and the sponsor (or designee) and reviewed by the site monitor.

Any major protocol deviation will be recorded in the eCRF along with the start date and details of the deviation.

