6.5 Pharmacokinetic (PK) Analysis Set

The Pharmacokinetic (PK) analysis set will include all subjects who received at least one dose of IMP, and have at least one post-dose evaluable plasma concentration.

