8.8 Protocol Deviations

Major protocol deviations, as recorded in the eCRF, will be listed.

9 Efficacy Analyses

Not applicable

10 Safety Analyses

The safety analysis will be conducted on the safety analysis set for each part separately. Safety variables to be analyzed include AEs, clinical laboratory assessments, vital signs,

Quabodepistat (OPC-167832)

Study 323-201-00007

12-lead ECGs, physical examinations, and the Columbia-Suicide Severity Rating Scale ([C-SSRS] Part 2 only). Descriptive statistics will be provided for the safety variables. Baseline measurements of safety variables are defined as the last measurement prior to the first dosing of IMP (also see [Section 6.7](#)).

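### SAP 6.4 limits the safety set to enrolled subjects, which under SAP 6.3 adds an eligibility condition that the protocol's safety population does not have

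*SAP*

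**What the plan says.** The two documents define the safety population differently.

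- **Protocol 9.2:** "The safety dataset includes all subjects who receive at least 1 dose of IMP". Protocol 9.4.3 repeats the rule for the tables: "Summaries will be based upon subjects who took at least 1 dose of IMP". Dosing is the only condition.
- **SAP 6.4:** "The safety dataset will include all enrolled subjects who have taken at least one dose of IMP". The word *enrolled* is added.
- **SAP 6.3:** "The enrolled analysis dataset includes all subjects that sign the informed consent form (ICF), and meet all eligibility criteria". This is the only place where the SAP says who belongs to the enrolled population.
- **SAP 6.5:** "The Pharmacokinetic (PK) analysis set will include all subjects who received at least one dose of IMP", provided there is also an evaluable post-dose concentration. The word *enrolled* does not appear.
- **SAP 10:** "The safety analysis will be conducted on the safety analysis set for each part separately". The safety set is also named for exposure (10.1), medical history (8.3), compliance (8.4) and concomitant medication (8.5).
- **SAP 15:** lists no change to the planned analysis.

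On eligibility, Protocol 5.2 rules out waivers: "Exceptions for eligibility criteria will not be permitted during the trial". Protocol 10.1.6 nevertheless gives as an example of a major deviation a "subject enrolled in violation of eligibility criteria or concomitant medication criteria", and provides for a joint decision by investigator and sponsor on whether that subject continues.

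**The concern.** Taken together, SAP 6.3 and 6.4 make eligibility a condition of entering the safety set. The protocol sets no such condition, and the SAP does not declare the difference.

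The subject at issue has been dosed and is later found to have breached an eligibility criterion. That subject is not a screen failure, because Protocol 5.4 reserves the term for consented subjects who are not assigned trial intervention. Under SAP 6.3 read literally the subject is not enrolled either. The SAP would then have no population in which to summarise this person's safety data, although the PK set would hold the concentrations from the same doses.

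Safety and tolerability is the trial's only secondary objective. With 12 subjects planned per part, one omitted subject can decide whether an event appears in a table at all.

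**Working it through.** The plan gives no figure to reproduce here. The check compares the definitions and then shows what one affected subject would do.

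**Step 1. Apply each rule to a subject who signed consent, was dosed, has an evaluable concentration, and breached one eligibility criterion.**

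| Rule | Conditions | Subject included? |
|---|---|---|
| Protocol 9.2 and 9.4.3, safety | at least one dose | Yes |
| SAP 6.3, enrolled | consent and all criteria met | No |
| SAP 6.4, safety, with *enrolled* read as in 6.3 | enrolled and at least one dose | No |
| SAP 6.4, safety, with *enrolled* read as entered into the trial | entered and at least one dose | Yes |
| SAP 6.5, PK | at least one dose and an evaluable concentration | Yes |

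The conflict with the protocol appears in the third row. It depends on reading *enrolled* as SAP 6.3 defines it.

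**Step 2. Size for one part.** Inputs: 12 subjects per part (Protocol 9.1, SAP 5), all assumed dosed. Let k be the number dosed but ineligible. The documents give no expected value of k, so k = 0, 1 and 2 are illustrations.

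Safety denominator under the literal reading = 12 − k. Share of the part left out = k/12.

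- k = 0: denominator 12, share 0/12 = 0%.
- k = 1: denominator 11, share 1/12 = 8.3%.
- k = 2: denominator 10, share 2/12 = 16.7%.

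**Step 3. Effect on a reported incidence, k = 1.** Suppose an event occurs only in the affected subject.

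- Protocol rule: 1/12 = 8.3%.
- SAP rule, literal: 0/11 = 0%.

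**Step 4. Effect on a zero count.** If nobody in the part has the event, the exact one-sided 95% upper bound on its incidence is 1 − 0.05^(1/n).

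- n = 12: 1 − 0.05^(1/12) = 22.1%.
- n = 11: 1 − 0.05^(1/11) = 23.8%.

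The loss of precision is small. What matters is Step 3, where an observed event disappears from the summary.

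**Step 5. What does not change.** AEs are recorded in source documents and the eCRF for every subject (Protocol 8.6.2), and immediately reportable events go to the sponsor within 24 hours (Protocol 8.6.3). Neither depends on an analysis set. SAP 8.1 counts treated subjects separately from enrolled ones, and SAP 8.8 lists deviations recorded as major. The primary PK analysis is unaffected.

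**The case against.** The strongest reply is that *enrolled* in SAP 6.4 is an ordinary word. The section does not name the Enrolled Analysis Set. Elsewhere the documents use the word to mean entered into the trial, as in the statements that 24 subjects are enrolled (SAP 3 and 5). Protocol 10.1.6 itself describes an ineligible subject as enrolled. On that usage SAP 6.4 keeps the subject and there is no conflict. This has force: the sponsor may never have intended the exclusion. But the SAP defines the enrolled population once, in the section immediately before, and in terms of eligibility. A programmer who follows the SAP has grounds to apply that definition.

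The second reply is that the case may never arise. Waivers are barred, criteria are checked at screening and again at check-in, and there is one site with 24 planned subjects. This stands as a limit on likelihood. It does not make the case hypothetical, since Protocol 10.1.6 provides for it.

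A reader might infer several stronger things that the documents do not support:

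- **That the subject's safety data would be lost.** They would be missing from summaries, but the eCRF record and expedited reporting remain.
- **That the subject would vanish from disposition.** SAP 8.1 names no analysis set and counts treated subjects. A gap between the treated count and the safety set would be visible.
- **That subjects who breach a criterion are the ones most likely to have safety problems.** No passage says so. Some Part 2 exclusions are safety screens, such as low blood counts, but others, such as lacking a permanent residence, are not clearly so.
- **That such subjects will be kept in the trial.** Protocol 10.1.6 requires a decision on continuation and does not say which way it goes.
- **That safety and PK denominators would otherwise agree.** They can differ anyway, because the PK set also needs an evaluable concentration.

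**Conclusion.** The definition in SAP 6.4 is wrong as written and should be fixed. Read with SAP 6.3, it narrows a safety population that the protocol defines by dosing alone, and SAP 15 does not declare the change.

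The consequence is conditional. It needs an ineligible subject to be dosed and *enrolled* to be applied as SAP 6.3 defines it. If both hold for one subject in a part of 12 dosed, that part's safety denominator is 11 instead of 12, and an event confined to that subject is reported as 0/11 instead of 1/12. If every dosed subject is eligible, no result changes.

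The documents do not show that the exclusion is intended or that it will happen. Safety is a secondary, descriptive analysis, and no hypothesis test is affected. That places the point at should-fix: a real conflict with a limited and conditional effect.

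**What to change.** Delete the word *enrolled* from SAP 6.4, so that the safety set is all subjects who have taken at least one dose of IMP, as in Protocol 9.2. The paragraph in 6.4 that says what IMP means in each part can stay.

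This settles the conflict without touching SAP 6.3. Revising 6.3 is optional. Protocol 9.2 defines no enrolled set, so nothing in it requires a change there. One practical consideration is that SAP 8.2 summarises demographics on enrolled subjects. If 6.3 is left alone, a dosed but ineligible subject could be in the safety tables but not in the demographic table. A footnote giving both counts would be enough.

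The cost is one word in the SAP. No new data, design change or clinical decision is needed.
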